2.4 Treatment/Assessment/Intervention and Duration

This is an observational study designed to (1) evaluate the feasibility and utility of digital health technology in a MOUD treatment population, and (2) capitalize on the availability of EHR data to relate passive and active sensing data to treatment retention and medication adherence. This feasibility study will be conducted rapidly (e.g., within 1 year plus time to data lock) to generate data that can inform other HEAL (Helping to End Addiction Long-termSM) Initiative studies and clinical trials of populations with OUD.

Eligible participants are identified through EHR records, sent an invitational letter through secure message, and then called to recruit and screen. Following verbal consent to screen, research staff will perform a screening assessment over the phone/video to determine preliminary study eligibility prior to scheduling the baseline phone/video visits. Following electronic signed informed consent, the Baseline assessment will consist of interviewer-administered measures examining participant characteristics, current substance use (e.g., tobacco, alcohol, opioids, and other drugs), and substance use and mental health disorders. In addition to the screening and baseline assessments, the participants will be asked to wear a smartwatch and carry a smartphone continuously for a period of 12 weeks. The smartwatch will passively collect data regarding distance traveled, physical activity (including metrics of energy expenditure and steps), sleep, and heart rate. Also, participants will be prompted to respond to questions through a smartphone (i.e., EMA) up to 3 times daily for 12 weeks. Responses to these questions (which include questions regarding sleep, stress, pain severity, pain interference, pain catastrophizing, craving, withdrawal, substance use risk context, mood, context, substance use, self-regulation, MOUD adherence, and impact of COVID-19) will take approximately 10 minutes to complete at each prompting. In addition to the EMA prompts, individuals will be asked to self-initiate EMAs if substance use occurred. The responses to the self-initiated EMAs will take roughly 5 minutes to complete. App usage, audio/conversation, call/text, GPS, screen on/off, phone lock/unlock, phone notification

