information, Wi-Fi & Bluetooth logs, sleep, ambient light, and proximity will be passively collected via smartphone. After the 12-week active study phase, participants complete a follow-up phone/video visit. At the follow-up phone/video visit, research staff will administer an interview-based assessment to measure current substance use (e.g., tobacco, alcohol, opioids, and other drugs), participant experience with the study devices (including wearing the smartwatch, carrying the smartphone, and responding to EMAs), treatment utilization, reasons for drop out (if appropriate), medication use/dose (if applicable), and overdose. For those who consent, social media data will be downloaded by the participant directly from the social media platform to a secure server using a remote desktop at the beginning of the study and at the end of the study. EHR and medical claims data (e.g., pharmacy claims data for Kaiser and non-Kaiser pharmacies if a claim was paid for) will be extracted 16 weeks after study completion (data will be collected 12 months prior to EMA start through 12 weeks after EMA start). Prior to each encounter (screening, baseline and follow-up), research staff will administer a brief prisoner status assessment to confirm study eligibility (non-prisoner status).

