Our approach to prediction will include regression-based methods (e.g., logistic regression), but we will also use common machine learning approaches for binary classification (e.g., random forest, support vector machines, K-nearest neighbor, gradient boosting). Although machine learning methods may often be more effective for prediction than regression-based methods, they may be difficult to explain, or may not reveal insights regarding the relationships between factors. Therefore, we also include a set of analyses that are conducive to generating such explanatory or descriptive insights. For example, we will apply supervised metric learning and prototypical case-based reasoning (Hsueh, Das, Maduri, & Kelly, 2018), topic-modeling (e.g., Latent Dirichlet Allocation) and causal inference methods (Hernan & Robins, 2006; Donald B. Rubin, 1974) (Kleinberg & Hripcsak, 2011). For detecting endpoints that currently rely on actively collected ecological momentary assessment, we will attempt to use only passively collected data to correctly classify whether the endpoint of interest has occurred.

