11.5 Digital Health Technology

11.5.1 Ambulatory Physiological Assessment using Mobile Sensors

We will develop a smartphone application, that can sense and store contextual information about a participant, e.g., location, physical activity (steps), phone activity (non-identified audio information such as segments of silence, speech features such as pitch control and voice quality), app usage, call/text, screen on/off, phone lock/unlock, sleep, ambient light, and proximity (e.g., to user's ear). Features will be derived from the raw sensing streams to create multiple relevant contextual variables. This application will be installed directly on the study provided smartphone (Moto G7 Power) or on a participant's smartphone (if they have a compatible phone). The data collected will be stored on the smartphone and will be securely transmitted to a secure cloud-based database hosted at Dartmouth.

In addition to the smartphone, the participants will be provided with a smartwatch (Garmin Vivosmart 4). The participants will be asked to wear the smartwatch continuously (except during pre-determined exceptions periods, such as when the participants are showering or charging the device). In our experience, the Garmin Vivosmart 4 smartwatch (among others) is comfortable, lightweight, and has a long battery life and an easy-to-use interface. The device can reliably track distance traveled, physical activity (including metrics of energy expenditure and step count), sleep stages, as well as heart rate. Data from the Garmin smartwatch includes raw sensor data, like, heart-rate, and several high-level features computed by Garmin (using their proprietary algorithms including; sleep stage information, periods of light/deep sleep, stress levels, and others). This data will be transmitted to the Garmin Connect application installed on the smartphone, which would in turn send the data to Garmin cloud servers. Garmin will provide us with access keys for the research staff to pull the data from the Garmin servers to the cloud-based database at Dartmouth College.

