11.5.2 Ecological Momentary Assessment (EMA)

Participants will be prompted up to 3 times per day over 12 weeks by the smartphone app to self-report sleep, stress, pain severity, pain interference, pain catastrophizing, craving, withdrawal, substance use risk context, mood, context, substance use, self-regulation, MOUD adherence, and the impact of COVID-19 (Buysse, Reynolds, Monk, Berman, & Kupfer, 1989; Freeman & Gottfredson, 2018; Kuerbis et al., 2019; Preston et al., 2017, 2018). The EMA prompt delivery times will be randomized within each of the prompt timeframes (e.g., morning, mid-day, end of day). In addition to prompted EMAs, participants will be asked to self-initiate EMAs if substance use occurred (e.g., opioids, cocaine, or other stimulants). All EMA data collected via the smartphone will be securely transmitted to a secure cloud-based database housed in the Research Computing Department at Dartmouth College.

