1. *Explaining temporal-causal relationships between factors determined to be useful for predicting outcomes:* Although machine learning methods may often be more effective for prediction than simple regression or correlation, they may be difficult to explain, or may not reveal insights regarding the relationships between factors. Therefore, we also include a set of analyses that are conducive to generating such explanatory or descriptive insights. For example, we will apply supervised metric learning and prototypical case-based reasoning (Hsueh et al., 2018), topic-modeling (e.g., Latent Dirichlet Allocation) and causal inference methods (Cheng, Bahadori, & Liu, 2014; Kleinberg & Hripcsak, 2011).
2. *Outcome detection using passively collected digital health data:* We plan to measure drug use and medication non-adherence events via EMA, multiple times a day. Since EMA requires a level of active engagement from participants that may not be realistic to expect outside of a research study, we plan to use machine learning to detect these events using only passively collected data. The methods used here would be similar to the machine learning methods previously described for binary classification.
3. *Feasibility of digital health technology:* We will generate descriptive statistical summaries of the level of adherence of study participants to the desired protocol (e.g., EMA response rate, smartwatch and smartphone wear/carry rate). No statistical inference is planned for this assessment.

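### Passive-only detection of drug use may partly detect the act of self-reporting, because phone-interaction logs record the self-initiated EMA session that supplies some of the labels

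*Combined protocol and SAP*

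**What the plan says.** **Labels.** Section 14.5 item 2 states: "We plan to measure drug use and medication non-adherence events via EMA, multiple times a day". Section 11.5.2 gives two routes. The first is scheduled: "Participants will be prompted up to 3 times per day over 12 weeks by the smartphone app to self-report". The second is participant-triggered: "participants will be asked to self-initiate EMAs if substance use occurred". Section 2.4 puts a self-initiated EMA at roughly 5 minutes. No other trigger for self-initiation is stated.

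**Features.** Section 14.5 item 2 says "we plan to use machine learning to detect these events using only passively collected data", and the synopsis has the same aim: "we will attempt to use only passively collected data to correctly classify whether the endpoint of interest has occurred" (Section 2.6). Section 2.4 lists the phone streams, beginning "App usage, audio/conversation, call/text, GPS, screen on/off, phone lock/unlock, phone notification" and ending "ambient light, and proximity will be passively collected via smartphone". Section 11.5.1 gives much the same list, including "app usage, call/text, screen on/off, phone lock/unlock, sleep, ambient light, and proximity", but without notifications. It says that features will be derived from the raw streams by an application on the study phone or the participant's own.

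**Purpose and metrics.** Item 2 is motivated by doubt that EMA engagement can be expected outside a research study. Section 14.5 names accuracy, precision, F-score, sensitivity and specificity as measures of prediction quality, and says that the detection methods will be similar.

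**The concern.** A self-initiated EMA is requested when substance use has occurred. Completing it means waking and unlocking the phone and using the study app for about 5 minutes with no prompt before it. All of that is visible in the streams the plan calls passive. A classifier given those streams can therefore learn that an unprompted study-app session goes with a positive label. It would do so without any sensor responding to drug use. This is target leakage.

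The trace exists only while participants are being asked to report. Item 2 is aimed at settings without EMA, where the trace disappears. Performance that rests on it would not carry over, and the planned metrics cannot separate detecting use from detecting reporting. Holding out participants would not expose it either, because the trace appears in anyone who self-reports. Section 2.4 says that the study is meant to inform other HEAL studies and trials, so an inflated result could be passed on.

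**Working it through.** The plan gives no event rate, performance target or sample-size figure for the detection analysis, so there is nothing to reproduce. The check has two parts.

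**1. Tracing label and features through the text**

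| Element | Where stated | Content |
|---|---|---|
| Label | 14.5 item 2; 11.5.2 | EMA reports, scheduled and self-initiated |
| Trigger for self-initiated EMA | 11.5.2; 2.4 | Substance use occurred |
| Features | 14.5 item 2; 2.6 | Passive data only; no stream excluded |
| Passive phone streams | 2.4; 11.5.1 | Include app usage, screen and unlock logs; notifications in 2.4 only |
| Device | 11.5.1; 11.5.2 | Sensing and EMA both run on the participant's smartphone |
| Removal of study-app activity, or cut-off before the report | Not found in any section supplied | – |

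The two label routes differ. Scheduled prompts number at most 3 × 7 × 12 = 252 per participant and arrive whether or not use occurred. Their trace is common to positive and negative windows and separates them little, except perhaps through session length. Self-initiation is asked for substance use, not for missed doses, so non-adherence labels have no matching trace.

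**2. Illustration of what the trace alone could yield**

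Take the rule: flag a window if the study app was opened outside a prompt session. Suppose no sensor carries any information on drug use. Let

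- p = share of windows with EMA-recorded use,
- s = share of those windows with a self-initiated EMA,
- f = share of non-use windows with an off-prompt opening.

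Then sensitivity = s, specificity = 1 − f, precision = ps / [ps + (1 − p)f], F = 2 × precision × s / (precision + s), and AUC for one binary feature = 0.5 + (s − f)/2.

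The documents give none of p, s or f; all values here are assumptions. With p = 0.05, s = 0.50 and f = 0.01:

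- true positives = 0.05 × 0.50 = 0.025; false positives = 0.95 × 0.01 = 0.0095; false negatives = 0.025
- precision = 0.025 / 0.0345 = 0.72
- F = 2 × 0.025 / (2 × 0.025 + 0.0095 + 0.025) = 0.050 / 0.0845 = 0.59
- AUC = 0.5 + 0.49/2 = 0.745

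With f = 0.05, false positives = 0.0475, precision = 0.025 / 0.0725 = 0.34, F = 0.050 / 0.1225 = 0.41 and AUC = 0.725. For comparison, a coin flip at p = 0.05 gives F = 0.050 / (0.050 + 0.475 + 0.025) = 0.09.

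F at p = 0.05:

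| s | f = 0 | f = 0.01 | f = 0.05 |
|---|---|---|---|
| 0.25 | 0.40 | 0.35 | 0.23 |
| 0.50 | 0.67 | 0.59 | 0.41 |
| 0.75 | 0.86 | 0.77 | 0.56 |

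Over p = 2–10%, s = 25–75% and f = 0–5%, F runs from 0.14 to 0.86 and AUC from 0.60 to 0.875. If the trace is removed, the rule cannot separate the windows: s = f, AUC = 0.50, and precision equals prevalence (0.05 in the central case).

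**The case against.** The strongest reply is that the leak is inferred. Item 2 lists no features, window length or timing, and Section 11.5.1 promises only relevant contextual variables. Nothing says that study-app openings or timing relative to prompts will be used. Section 14.7 defers detail to an Extended Data Analytic Plan that is not among the documents and might contain an exclusion. Section 14.5 also plans SHAP, mutual information and performance by feature category, which could show a dominant app-opening feature. The study is a pilot not powered to test specific hypotheses, and its primary objective is feasibility.

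Much of this stands. It limits the point to a possibility of unknown size in a non-primary analysis. It does not remove it: the stated feature set is passive data without exception. High importance for app usage or screen activity could also be read as behaviour that accompanies use.

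The illustration is sensitive to its inputs. Section 11.5.2 asks for self-initiation after other drugs too, whereas the use outcomes in Sections 7.2 and 7.3 concern non-prescribed opioids. For those outcomes, reports of other drugs count as false positives. Staff troubleshooting contacts (Section 8.3) could add further off-prompt openings. Both push f up and F down.

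A reader might infer more than the text allows:

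- **That the passive features contain the label outright, so detection results would be worthless.** The documents do not fix the features, and the harm depends on how far a model relies on the trace.
- **That every prompted EMA leaks in the same way, or that missed-dose detection is equally affected.** Prompts occur regardless of use, and no self-initiated EMA is requested for missed doses.
- **That the statement of no data editing in Section 16.5 rules out a filter.** That section is about data cleaning, not feature selection.

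**Conclusion.** The concern holds for self-initiated substance-use reports. As written, item 2 permits features that record the reporting session itself, and no supplied section excludes them. Precision, recall and F-score for drug-use detection could therefore be inflated by a signal that is absent where the detector is meant to work. The size cannot be computed from the documents. Under the central assumptions the trace alone gives F of about 0.59, falling to 0.41 when off-prompt openings rise from 1% to 5% of non-use windows. These figures show that the effect need not be trivial; they do not estimate it. The point should be settled before the detection analysis is run. If the Extended Data Analytic Plan already excludes this activity, a reference to it in Section 14.5 would answer the exclusion part.

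**What to change.** In Section 14.5 item 2, state that:

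1. Study-app and Garmin Connect records are removed from the app-usage and notification logs before features are derived.
2. For every window, event or non-event, features use only data ending a fixed, pre-stated margin before the labelling EMA session opens.
3. Screen and unlock activity from any other EMA session inside the window is removed, and rates are computed over the remaining time, so that the gap is not itself a feature.
4. Performance is reported with and without phone-interaction features, and separately for self-initiated and prompted labels.

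Simply blanking a margin on both sides of every EMA would be a poorer choice. An extra blank outside the prompt slots would itself mark a self-initiated report. It also costs more than it seems. With an assumed 15 minutes on each side and the roughly 10 minutes per prompted EMA in Section 2.4, each prompt loses 40 minutes. Three prompts lose 120 minutes a day, which equals 25% of the 8-hour minimum carry time in Section 11.2.

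The cost of the proposed change is some phone-use data closest to each report, where real signal may also lie, and a little more analysis work. Data collection, participant burden and consent do not change.

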14.6 Interim Analysis

No planned interim analyses.

14.7 Exploratory Analysis

See Extended Data Analytic Plan for more details.

14.8 Missing Data and Dropouts

Missing data will be classified into three classes according to the characteristics of the randomness: missing not at random (MNAR), missing at random (MAR), and missing completely at random (MCAR). Little's MCAR test will be applied to identify if the characteristics of the missing variable are (Little, 1988). For the other two types, we will make use of the tests for interactions between observed variables. If a significant interaction exists, that will be treated as MNAR data. Missing samples will be imputed using previously suggested well-known approaches suitable for the category of the missing variable (Sarker, Tyburski, Rahman, et al., 2016).

14.9 Demographic and Baseline Characteristics

Descriptive summaries of the distribution of continuous baseline variables will be presented with percentiles (median, 25th and 75th percentiles), and with mean and standard deviation. Categorical variables will be summarized in terms of frequencies and percentages.

14.10 Safety Analysis

Not applicable, as no treatment/intervention is being provided for this study.

15.0 REGULATORY COMPLIANCE, REPORTING and MONITORING

15.1 Statement of Compliance

This study will be conducted in accordance with the current version of the protocol, in full conformity with the ethical principles outlined in the Declaration of Helsinki, the Protection of Human Subjects described in the International Council for Harmonization Good Clinical Practice (GCP) Guidelines, applicable United States (US) Code of Federal Regulations (CFR), the NIDA Terms and Conditions of Award, and all other applicable state, local, and federal regulatory requirements. The Principal Investigators will assure that no deviation from, or changes to the protocol will take place without prior agreement from the Sponsor and documented approval from the Institutional Review Board (IRB), except where necessary to eliminate an immediate hazard(s) to the trial participants. An Operations Manual will be provided as a reference guide and study quality assurance tool.

15.2 Institutional Review Board Approval

Prior to initiating the study, participating site investigators will obtain written approval from the Ethics Review Committee (ERC) or Institutional Review Board (IRB) to conduct the study at their respective site, which will include approval of the study protocol. If changes to the study protocol become necessary, protocol amendments will be submitted in writing by the investigators for IRB approval prior to implementation. In addition, IRBs will approve all consent forms, recruitment materials, and any materials given to the participant, and any changes made to these documents throughout study implementation. Approval of both the protocol and the consent form(s) must be obtained before any participant is consented. For changes to the consent form, a decision will be made regarding whether previously consented participants need to be re-consented. IRB continuing review will be performed annually, or at a greater frequency contingent upon the complexity and risk of the study. Each Site Principal Investigator is responsible for maintaining copies of all current IRB approval notices, IRB-approved consent documents, and approval for all protocol modifications. These materials must be received by the investigator prior to the initiation of research activities at the site and must be available at any time for audit. Unanticipated problems (UP) involving risk to study participants will be promptly reported to and reviewed by the IRB of record, according to its usual procedures.

The Kaiser Permanente Northern California Institutional Review Board will be the single IRB of record for the protocol and will provide study oversight in accordance with 45 CFR 46. Participating institutions will agree to rely on Kaiser IRB and will enter into reliance/authorization agreements for Protocol CTN-0084-A2. Kaiser IRB will follow written procedures for reporting its findings and actions to appropriate officials at each participating institution.

15.3 Informed Consent

The informed consent process is a means of providing study information to each prospective participant and allows for an informed decision about participation in the study. Informed consent continues throughout the individual's study participation. The informed consent form will include all of the required elements of informed consent and may contain additional relevant consent elements and NIDA CCTN specific additional elements. Each study site must have the study informed consent approved by Kaiser IRB. Prior to initial submission to the IRB and with each subsequent consent revision, the consent form must be sent to the Lead Node to confirm that each consent form contains the required elements of informed consent as delineated in 21 CFR 50.25(a) and CFR 46.116(b), as well as pertinent additional elements detailed in 21 CFR 50.25(b) and 45 CFR 46.116(c) and any applicable CCTN requirements. Every study participant is required to sign a valid, IRB-approved current version of the study informed consent form prior to the

initiation of any study related procedures. The site must maintain the electronically signed informed consent for every participant on a secure server located at Kaiser that is in compliance with all applicable IRB and institutional policies and that is accessible to the study monitors. Every study participant should be given a copy of the signed consent form.

During the informed consent process, research staff will explain the study to the potential participant by phone/video and provide the potential participant with a copy of the consent form to read and keep for reference. All participants will receive a verbal explanation in terms suited to their comprehension of the purposes, procedures, and potential risks of the study and their rights as research participants. Extensive discussion of risks and possible benefits will be provided to the participants. Participants will have the opportunity to carefully review the consent form and ask questions prior to signing. The participants should have the opportunity to discuss the study with their family and close friends or think about it prior to agreeing to participate. If the participant is interested in participating in the study, a qualified staff member will review each section of the IRB-approved informed consent form in detail and answer any questions the participant may pose. The participant will consent by providing an electronic date and signature. The person obtaining consent and a witness, if required by the IRB of record, will also electronically sign and date the consent document. It is strongly recommended that another research staff member review the consent after it is signed to ensure that the consent is properly executed and complete. Staff members delegated by the PI to obtain informed consent must be listed on the Delegation of Responsibility and Staff Signature Log and must be approved by the IRB, if required. All persons obtaining consent must have completed appropriate GCP and Human Subjects Protection training, as mandated by NIDA standard operating procedures.

The informed consent form must be updated or revised whenever important new safety information is available, or whenever the protocol is amended in a way that may affect participants' participation in the trial. The rights and welfare of the participants will be protected by emphasizing to them that the quality of their medical care will not be adversely affected if they decline to participate in this study. The participant will be informed that their participation is voluntary, and they may withdraw from the study at any time, for any reason without penalty. Individuals who refuse to participate or who withdraw from the study will be treated without prejudice. The study site will be responsible for maintaining electronically signed consent forms as source documents for quality assurance review and regulatory compliance.

